9.5.9 Sub-Group Analyses

Not applicable.

9.5.10 Tabulation of individual Participant Data

Safety data will be presented by line listing and tables at the individual level, as described in section 9.5.5.

9.5.11 Exploratory Analyses

To explore the impact of L9LS on the genotype of infection -inducing parasites at the CSP locus, a genotypic sieve analysis will be performed to analyze CSP sequences of breakthrough parasites in the blood samples of infected subjects. The sieve analysis will differentiate protective efficacy against different genotypes of infection-inducing parasites with genotype defined by, for example, number of mismatches to the L9LS footprint. To explore whether receipt of MAb affects development of measles-specific antibodies among those who receive the measles vaccine after their first MAb dose, mean and median antibody titers will be compared among subjects <9 months of age at enrollment, prior to and after receipt of MAb. The exploratory analysis comparing one versus two doses of L9LS against Pf infection and clinical malaria will be done as outlined in section 9.5.4 above.

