| To assess the impact of L9LS on hospitalizations with malaria To determine whether ADA to L9LS can be detected in sera of recipients at specific timepoints throughout the study. To assess for IgG1 allotypes and allotype specific effects on L9LS PK. To determine if the efficacy of L9LS is specific to certain | Proportion of participants hospitalized with malaria Measurement of ADA to L9LS in sera of recipients. Assessment of IgG1 allotypes and allotypespecific effects on L9LS PK. CSP genotyping of parasites isolated from study subjects. Pre-existing parasitemia detected by microscopic examination of thick | It is possible that L9LS might not prevent malaria but might prevent the progression to severe malaria. ADA to L9LS may impact the PK and activity of L9LS. Subject IgG1 allotype may impact the PK and activity of L9LS. L9LS efficacy may be specific to certain |

| OBJECTIVES | ENDPOINTS | JUSTIFICATION FOR |
|---|---|---|
| | | ENDPOINTS |
| Pf parasite genotypes at the CSP locus. | blood smears or RT-PCR before L9LS | Pf parasite genotypes at the CSP locus. |
| 5. To explore the impact of pre-existing parasitemia on the protective efficacy and PK of L9LS. | administration. 6. Pre-existing CSP-specific antibodies measured in sera collected before L9LS administration. | 5. Pre-existing parasitemia may impact the protective efficacy and PK of L9LS. |
| 6. To explore the impact of pre-existing CSP antibodies on the protective efficacy and PK of L9LS. | 7. Measles virus-specific IgG antibodies among subjects <9 months of age at | 6. Pre-existing CSP-specific antibodies may |
| 7. To assess the effect of L9LS on antibodies to measles in the younger age group. | enrollment. 8. Pf infection and clinical malaria over 12 months. | impact the protective efficacy and PK of L9LS. |
| 8. To compare the efficacy of one versus two doses of L9LS against Pf infection and clinical malaria over 12 | | 7. Address concerns that L9LS might impact immune response to measles vaccine. |
| months. | | 8. Pf infection and clinical malaria are our primary and secondary endpoints. |
| Follow-on Study Primary Object | etives | |
| Follow-on Safety (part 1b) 1. To evaluate the safety and tolerability of L9LS | Incidence and severity of local and systemic AEs occurring within 7 days after the administration of | 1. Assessment of AEs is a standard measure of study agent safety and tolerability. |

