This will be a phase 2, double-blind, randomized, controlled clinical trial to evaluate the efficacy of L9LS against malaria infection among children ages 5 to 59 months in a setting of perennial high transmission. Participants will be stratified by age group (5-17 months and 18-59 months) and within each age group randomly assigned in a 2:1 ratio to receive L9LS or placebo as an initial injection. The two age groups will be enrolled in parallel. Study arms are as follows:

- 1. L9LS at 10-20 mg/kg (SC administration):
 - a. 5-17 months of age
 - i. L9LS dose 2 at 6 months
 - ii. Placebo dose 2 at 6 months

- b. 18 months to 59 months of age
 - i. L9LS dose 2 at 6 months
 - ii. Placebo dose 2 at 6 months

2. Placebo arm:

- a. 5-17 months of age (with placebo dose 2 at 6 months)
- b. 18 months to 5 years of age (with placebo dose 2 at 6 months)

After an initial screening, we will obtain informed consent from those eligible; for those consenting, we will conduct a more complete screening that includes a physical exam and blood draw to assess parasitemia, hematological and biochemistry values, antimalarial antibody and antigen titers, and other parameters; for those who remain eligible, we will administer a full, weight-based course of DP, the second-line antimalarial in Kenya, to clear parasites. (For children who have taken an antimalarial within the last 2–4 weeks, this antimalarial course will be deferred at least 7 days from the date of the last dose of AL or at least 4 weeks after the last dose of DP.) Between 14 and 21 days after the first dose of DP (considered day 1 for dosing window), children will return and then be randomized to receive a SC injection(s) of either placebo or L9LS, according to study arm. Children will be considered enrolled once they are randomized on the Day 0 dosing visit. We will use a 'constrained' fixed dosing approach that ensures each child receives a minimum of 10 mg/kg in a relatively simple dosing scheme. See section 6.2.4 for exact dosing information and the number of required injections of two syringe types for various participant weights.

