9.2.2 Sample Size Considerations for the Efficacy Study

Table 6 shows initial sample size estimations powered to detect a 70% vaccine efficacy (1 – [proportion infected in L9LS/proportion infection in control]) at 12 months comparing L9LS at 10-20 mg/kg to placebo. Sample size calculations were done assuming the endpoint of any Pf infection will be calculated using a proportional analysis, 80% or 90% power, an alpha of 0.05, and that either 30%, 35%, or 40% of children in the placebo group are infected at 6 months and that 40% or 45% are infected at 12 months. (Time-to-event analyses typically require smaller sample sizes.) The primary endpoint will be at 12 months and will combine both MAb age groups who received two doses of L9LS and compare those subjects to the overall placebo group, i.e., we will assess MAb efficacy among children 5–59 months. However, the trial sample size is based on the secondary endpoint of 12-month MAb efficacy with two doses among the younger age group (5–17 months) versus the 5–17-month-old subjects in the placebo group, as these will require larger sample sizes than the primary endpoint. Factoring in 25% loss to followup over 12 months, and a doubling of the sample size in each intervention arm to allow for comparison of L9LS with a second dose (at 6 months) to placebo and comparison of L9LS without a second dose to placebo would require 108 children in each L9LS group and 54 children in the placebo arm, assuming 35% infected in the placebo group at 6 months.

Abbreviated Title: Anti-malaria MAb in Kenyan children

Version 6.0 Date: 2 Apr 2024

Table 6. Sample size calculations based on secondary 12-month endpoint, to achieve 80% power to detect efficacy of 70% at 6 months and 60% at 12 months, assuming 35% of the control group are infected by 6 months and 45% by 12 months.

| Arm | Assumed proportion infected in control group by 6 mos | mAb Efficacy at 6 months | Power | Number needed at 6 months | | Assumed % infected in control group by 12 mos | mAb Efficacy at 12 months | Number needed at 12 months | Number needed to enroll | Number with 20% LTFU* |
|------------------------------|---|-----------------------------------|----------|---------------------------------|-----|---|------------------------------------|-------------------------------------|-------------------------------|-----------------------|
| mAb 5-17 mos + Dose 2 | 0.30 | 70% | 80% | 50 | 120 | 0.40 | 60% | 52 | 104 | 130 |

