APPENDIX A: KENYA NATIONAL IMMUNIZATION SCHEDULE

NATIONAL IMMUNIZATION SCHEDULE

Kenya

Recommended routine immunization

| Vaccine | Description | Schedule | Comments | | | | |
|--|---|--|---|--|--|--|--|
| Primary Infant and Adolescent Vaccination Schedule | | | | | | | |
| BCG | Bacille Calmette-Guérin vaccine | Birth | | | | | |
| OPV | Oral polio vaccine | Birth; 6, 10, 14 weeks | | | | | |
| Rotavirus | Rotavirus vaccine | 6, 10 weeks | | | | | |
| Pneumo_conj | Pneumococcal conjugate vaccine | 6, 10, 14 weeks | | | | | |
| DTwPHibHepB | Diphtheria and Tetanus and Pertussis and Haemophilus influenzae and Hepatitis B vaccine | 6, 10, 14 weeks | | | | | |
| IPV | Inactivated polio vaccine | 14 weeks | | | | | |
| YF | Yellow fever vaccine | 9 months | Not available in all parts of the country | | | | |
| Measles | Measles vaccine | 9, 18 months | | | | | |
| HPV | Human Papillomavirus vaccine | 10 years; +6 months | From january 2018 | | | | |
| Adult Vaccination Schedule | | | | | | | |
| HepB_Adult | Hepatitis B adult dose vaccine | 1 st contact; +1, +1 months | High risk groups (e.g. health workers) | | | | |
| тт | Tetanus toxoid vaccine | 1 st contact pregnancy; +1, +6 months; +1, +1 year | | | | | |
| Vaccines for Travellers | | | | | | | |
| Typhoid | Typhoid fever vaccine | 1 st contact travellers | | | | | |

Reference: Modified from World Health Organization (WHO)

Date accessed: 29 March 2018

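### The measles-antibody analysis compares titres before and after MAb, so it cannot separate an effect of L9LS from the routine measles vaccine and age; no L9LS-versus-placebo comparison of measles titres is planned

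*Combined protocol and SAP*

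**What the plan says.** Exploratory objective 7 in section 3 reads "To assess the effect of L9LS on antibodies to measles in the younger age group", and the reason given is "Address concerns that L9LS might impact immune response to measles vaccine". Section 9.5.11 restricts the question to infants "among those who receive the measles vaccine after their first MAb dose" and then gives one comparison: "mean and median antibody titers will be compared among subjects <9 months of age at enrollment, prior to and after receipt of MAb". It names neither a comparator arm nor the draw that counts as after.

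Other relevant text:
- Appendix A gives the routine timing: "Measles vaccine | 9, 18 months".
- The Part 2 schedule (section 1.4.2) takes serum at pre-enrolment, Day 28, Day 196 and Day 336. The second injection is at Day 168.
- Section 4.1 has children "within each age group randomly assigned in a 2:1 ratio to receive L9LS or placebo as an initial injection". For the 5-17 month stratum, section 9.2.2 says the design "would require 108 children in each L9LS group and 54 children in the placebo arm".
- Section 2.2.2 plans research assays in placebo controls as well as L9LS recipients.
- Section 9.5.1 has a general rule that descriptive statistics are tabulated by arm.

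**The concern.** The objective is causal: how does the measles response with L9LS compare with the response without it? A before/after change within L9LS recipients has no reference for the rise that vaccination and age would produce anyway. A clear rise is compatible with no L9LS effect and also with partial blunting of the vaccine response. The protocol itself raised this concern about a routine childhood vaccine. An analysis that cannot detect partial interference would leave it open while appearing to have addressed it.

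**Working it through.** **1. Does vaccination fall between the samples?** At 30.4 days per month, Day 28 is 0.9 months after enrolment, Day 196 is 6.4 months and Day 336 is about 11 months.

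| Age at enrolment | Day 28 | Day 196 | Day 336 |
|---|---|---|---|
| 5 months | 5.9 | 11.4 | about 16 |
| just under 9 months | just under 9.9 | just under 15.4 | about 20 |

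The pre-enrolment sample precedes both MAb and vaccine. At Day 28 most of these infants are not yet due for vaccine, and those who are have only just reached 9 months. By Day 196 all are past 9 months and none has reached 18. By Day 336, those enrolled at about 7 months or older (18 - 11 = 7) may have had the second measles dose. Day 196 is therefore the clean post-vaccination draw.

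**2. What does each comparison estimate?** On the log scale:
- before/after in L9LS infants = vaccine + age/time + L9LS effect
- the same change in placebo infants = vaccine + age/time
- the difference between arms = L9LS effect

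Only the difference between arms isolates L9LS.

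**3. Numerical illustration.** The documents give no measles titre, expected rise or SD, so these inputs are assumptions: SD of log10 change 0.5, 33 L9LS and 17 placebo infants, 4,000 simulated trials, two-sided 0.05.

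| Vaccine rise (log10) | L9LS effect (log10) | Before/after estimate | Before/after significant | Between-arm estimate | Between-arm significant |
|---|---|---|---|---|---|
| 0.5 | 0 | +0.50 | 100% | 0.0 | 5% |
| 0.5 | -0.3 | +0.20 | 59% | -0.30 | 51% |
| 0.2 | -0.3 | -0.10 | 21% | -0.30 | 49% |

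In the second row a real reduction is hidden behind a rise. In the third the reduction exceeds the vaccine rise and the titre falls. The sign of the before/after change thus depends on a vaccine effect that this analysis does not estimate.

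**4. How precise would the comparison between arms be?** The plan states no sample size or power for the measles question, so there is no figure to reproduce. Assume ages are uniform over the 13 monthly ages from 5 to 17; ages 5 to 8 then make up 4/13.
- L9LS: 108 x 4/13 = 33. Placebo: 54 x 4/13 = 17.
- Detectable difference in SD units at 80% power = (1.96 + 0.84) x sqrt(1/n1 + 1/n2).
- No loss, 33 v 17: 2.80 x sqrt(1/33 + 1/17) = 0.84 SD.
- 20% loss (Table 6), 27 v 13: 2.80 x sqrt(1/27 + 1/13) = 0.95 SD.
- 25% loss (text of section 9.2.2), 25 v 12: 2.80 x sqrt(1/25 + 1/12) = 0.98 SD.

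For an assumed SD of log10 change of 0.3 to 0.6, the detectable titre ratio is 1.8- to 3.2-fold with no loss and 2.0- to 3.9-fold with 25% loss. If the under-9-month share is 10% (11 v 5, no loss) it is 2.8- to 8.1-fold; at 50% (54 v 27) it is 1.6- to 2.5-fold.

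**The case against.** The best defence is that the text is under-specified rather than wrong. Placebo samples are to be assayed (section 2.2.2), and section 9.5.1 tabulates endpoints by arm with confidence intervals. The sentence in 9.5.11 could be read as arm summaries before and after dosing. This stands in part: a reader might infer that placebo infants play no role, and the documents do not go that far. But the only comparison named is around receipt of MAb, which placebo infants never receive, and a general tabulation rule is not a planned contrast.

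The analysis is also exploratory, and section 9.5 promises a detailed SAP before unblinding that will take precedence. Both points are true. Exploratory status excuses low power, but not an estimate that cannot answer its own question. The later SAP is not in the documents; it is the natural place for the correction.

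Three limits on the alternative also stand:
- The comparison between arms is not perfectly unconfounded if restricted to vaccinated infants, because vaccination comes after randomisation. Blinding (section 6.3.2), and a limit on vaccines near dosing that applies to both arms (section 6.5), make differential uptake unlikely but do not exclude it.
- The first sample after vaccination, whatever its day, would be a poor choice: for an infant enrolled at 8 months it could be a Day 28 sample taken too soon after vaccination.
- Day 196 follows the Day 168 injection, so a pooled L9LS group mixes one-dose and two-dose infants.

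**Conclusion.** The point holds. The stated comparison cannot identify the effect of L9LS on the measles response, and no comparison of L9LS with placebo is planned for measles titres, although randomised placebo infants of the same age are in the trial.

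A reader might go further and infer that even a large blunting would show as a rise and be taken as reassuring. The documents do not support that: they give no expected rise, and blunting larger than the rise would show as a fall. What can be said is that partial blunting could be hidden.

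Nor should 0.84 SD be read as the precision the trial will have. It assumes uniform ages and no loss; with 25% loss it is about 0.98 SD. Exclusion criterion 5 (section 5.2) may shrink the subgroup further. With RTS,S anticipated in June 2023 and enrolment expected to run to February 2023 (section 5.7), an infant enrolled in February would need to be about 8 months old (12 - 4 = 8). Section 5.2 also allows for excluding all children under 12 months, which would leave no such infants.

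No primary or secondary conclusion depends on this analysis.

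**What to change.** In the SAP, before unblinding:
- Make the main exploratory measles comparison L9LS versus placebo, among infants under 9 months at enrolment who were vaccinated after their first injection. Use log measles IgG at a fixed draw, Day 196, adjusted for pre-enrolment titre and age.
- Report the geometric mean ratio with its 95% CI rather than relying on a test.
- Record vaccination dates, and report uptake and timing by arm.
- As a check on conditioning on vaccination, repeat the comparison in all infants under 9 months at enrolment, whether or not vaccinated.
- Show one-dose and two-dose L9LS infants separately as well as pooled.
- Keep the before/after figures as description, by arm.
- State the number of infants under 9 months actually enrolled and the precision that follows.

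The cost is SAP wording and at most a few measles assays on stored placebo serum, which section 2.2.2 suggests are already planned. No new blood draw is needed.

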10 REGULATORY AND OPERATIONAL CONSIDERATIONS

10.1 Informed Consent Process

10.1.1 Consent/Assent Procedures and Documentation

As this study will include only children 10 years of age and younger, informed consent/permission will be obtained from parents or guardians prior to any study procedure. All consent forms will be translated into Dholuo and Kiswahili and back translated into English to ensure accuracy.

The consent form will detail the design of the study, the intervention (vaccination with L9LS or placebo), collection of blood samples, and study requirements for follow-up. A designated and trained study staff will describe the protocol to potential participants' parent(s)/guardian(s) face to face, the informed consent form will be read together with the participants' parent(s)/guardian(s), and the participants' parent(s)/guardian(s) shall be given ample opportunity to inquire about details of the study and ask any questions, including from clinical staff, before dating and signing (or thumbprinting, in the case of illiterate persons) the informed consent form. Consenting of an illiterate parent/guardian will be performed in the presence of an impartial witness who will sign the consent/permission form on behalf of the parent/guardian. The illiterate parent/guardian will be asked to sign or place their thumbprint on the consent form to document their consent/permission.

Details about the trial and its benefits and potential risk will be explained to the parent/guardian in the language in which they are most fluent. All information regarding the participants will remain confidential to the extent allowed by law. Unique numerical identifiers will be used for data entry.

The storage of blood samples will then be explained to the parents or guardians. If they agree to have their child's blood samples stored at KEMRI, each individual will be asked to sign consent to store samples. Permission will also be sought for shipping of some samples to the NIH and other collaborating laboratories in the US for immunologic testing and parasite genotyping. All parents/ guardians will be provided with a signed consent form after they have agreed to participate in the study. Should a parent/guardian prefer not to keep a copy of the consent form, this will be documented. Should the consenter be non-medical personnel, a clinical/medical officer or nurse will be available to answer further questions.

Each parent's/guardian's signed informed consent form will be kept on file by the investigator for possible inspection by regulatory authorities. Any amendments to the written information will be provided to participants' parents/guardians.

10.1.1.1 Justification for Alteration of Informed Consent

Due to the high illiteracy rate in the area, we are seeking an alteration of informed consent to accept a witnessed thumbprint in lieu of a signature for parent(s)/guardian(s) who cannot sign their names.

10.2 Study Discontinuation and Closure

The study may be temporarily suspended or permanently terminated as described in the halting rules (section 8.4.6). In addition to the reporting described in that section, the principal investigator(s) will promptly contact the study subjects, provide the reason(s) for the termination or suspension, and, if applicable, inform them of changes to study visit schedule.

The principal investigators will consult with the IRBs prior to resuming the study following a halt.

10.3 Confidentiality and Privacy

All records will be kept confidential to the extent provided by federal, state, and Kenyan law. The study monitors and other authorized representatives of the sponsor may inspect all documents and records required to be maintained by the investigator, including but not limited to, medical records. Records will be kept in the study clinics and/or KEMRI-CGHR under key and lock and data will be coded. Any personally identifiable information maintained for this study will be kept on restricted-access computers and networks. Personally identifiable

information will only be shared with individuals authorized to receive it under this protocol. Individuals not authorized to receive personally identifiable information will be provided with coded information only, as needed. Clinical information will not be released without written permission of the subject, except as necessary for monitoring by the IRBs, FDA, NIAID, Office for Human Research Protections (OHRP), the VRC, or the sponsor's designee.

To further protect the privacy of study subjects, a Certificate of Confidentiality has been issued by the NIH. This certificate protects identifiable research information from forced disclosure. It allows the investigator and others who have access to research records to refuse to disclose identifying information on research participation in any civil, criminal, administrative, legislative, or other proceeding, whether at the federal, state, or local level. By protecting researchers and institutions from being compelled to disclose information that would identify research subjects, Certificates of Confidentiality help achieve the research objectives and promote participation in studies by helping assure confidentiality and privacy to subjects.

Samples and data will be collected and stored under this protocol. All of the stored study research samples are labeled by a code that only the investigators can link to the subject. Samples are stored in secure research laboratories in locked freezers with limited access at the KEMRI, and the NIH. Data will be kept in password-protected computers. Only investigators or their designees will have access to the samples and data.

Samples and data acquired under this protocol will be tracked using BSI Systems software.

Any loss or unanticipated destruction of samples (for example, due to freezer malfunction) or data (for example, misplacing a printout of data with identifiers) that meets the definition of a reportable event will be reported to the IRBs.

Additionally, subjects may decide at any point before the end of the trial not to have their samples stored. In this case, the principal investigator will destroy all known remaining samples and report what was done to both the subject and to the IRBs. This decision will not affect the individual's participation in this protocol or any other protocols at NIH.

